3.3.1.4. Progression-free survival (PFS) as assessed by BIRC

PFS is defined as the interval from the start of acalabrutinib therapy to the earlier of the first documentation of objective disease progression by the BICR or death from any cause.

Subjects who withdraw from the study or are considered lost to follow-up without prior documentation of disease progression will be censored on the date of the last adequate disease assessment. Subjects who start new anticancer therapy before documentation of disease progression will be censored on the date of the last adequate disease assessment that is on or before the start date of the new anticancer therapy. For patients without an adequate post-baseline disease assessment or no baseline assessments, PFS will be censored on the date of randomization unless they die within 2 visits of baseline.

Table 6 Censoring rules for PFS

Assessment	Outcome	Date of progression or censoring
Death before first disease assessment	Event	Date of death
Documented PD between scheduled visits on or before receiving subsequent anticancer therapy or data cutoff, whichever occurred first	Event	Earliest date of disease assessment documenting progression
Death without documented PD and not receiving subsequent anticancer therapy on or before data cutoff	Event	Date of death
No baseline tumor assessments and it's not known to have died in 2 consecutive visits of baseline	Censored	Date of first dose
No adequate post-baseline assessment and it's not known to have died in 2 consecutive visits of baseline	Censored	Date of first dose
Documented PD or death after subsequent anticancer therapy and the subsequent anticancer started before data cutoff date	Censored	Date of last adequate disease assessment prior to subsequent anticancer treatment
No documented PD or death at the time of data cutoff and subsequent anticancer therapy started before the data cutoff	Censored	Date of last adequate disease assessment prior to subsequent anticancer treatment
Documented PD or death after subsequent anticancer therapy and the subsequent anticancer started after data cutoff date	Censored	Date of last adequate disease assessment on or before data cutoff
No documented PD or death at the time of data cutoff and subject not received subsequent anticancer therapy or subsequent anticancer therapy started after the data cutoff	Censored	Date of last adequate disease assessment on or before data cutoff
Withdrew consent without documented PD or death	Censored	Date of last adequate disease assessment
Lost to follow-up without documented PD or death	Censored	Date of last adequate disease assessment
Documented PD or death after 2 or more consecutively missed visits	Censored	Date of last adequate disease assessment before the consecutively missed visits

PD = progressive disease

3.3.1.5. Time to response (TTR) as assessed by BIRC

TTR will be analyzed for subjects with objective response (PR or better) and is defined as the interval between the date of first dose and the date of initial documentation of a response.

Time to initial response as well as time to best response (in the order of CR > PR for r/r MCL and CR > CRi > nPR > PR for r/r CLL) will be derived.

3.3.1.6. Investigator-assessed endpoints (ORR, DoR, PFS and TTR)

Definition of ORR, DoR, PFS and TTR by the investigator assessment will follow BICR assessed endpoints as above.

3.3.1.7. Overall survival (OS)

OS is defined as the interval from the start of acalabrutinib therapy to death from any cause. Subjects who are known to be alive as of their last known status will be censored at their last date known to be alive.

Table 7 Censoring rules for OS

Assessment	Outcome	Date of progression or censoring
Death on or before data cutoff	Event	Date of death
Alive before data cutoff	Censored	Date subject last known to be alive
Death after data cutoff	Censored	Date of data cutoff
Alive on or after data cutoff	Censored	Date of data cutoff
Withdrew consent prior to data cutoff	Censored	Date of discontinuation from study participation as reported on study exit CRF
Lost to follow-up prior to data cutoff	Censored	Date subject last known to be alive

3.3.1.8. Time to Next Treatment (TTNT, for R/R CLL only)

TTNT is defined as the interval from the start of acalabrutinib therapy to institution of non-protocol specified anti-cancer treatment for CLL or death due to any cause, whichever comes first. Data from surviving subjects who do not receive any non-protocol specified treatment will be censored at the last time that lack of non-protocol specified treatment was objectively documented.

Table 8 Censoring rules for TTNT

Assessment	Outcome	Date of progression or censoring
Next treatment or death on or before data cutoff	Event	Earliest date of next treatment or death
Do not receive next treatment and alive on or before data cutoff	Censored	Last time that lack of non-protocol specified treatment
Next treatment and alive after data cutoff	Censored	Date of data cutoff
Next treatment and death after data cutoff	Censored	Date of data cutoff

Table 8 Censoring rules for TTNT

Assessment	Outcome	Date of progression or censoring
Do not receive next treatment at any time and death after data cutoff	Censored	Date of data cutoff
Do not receive next treatment at any time and alive after data cutoff	Censored	Date of data cutoff
Withdrew consent without next treatment prior to data cutoff	Censored	Date of discontinuation from study participation as reported on study exit CRF
Lost to follow-up without next treatment prior to data cutoff	Censored	Last time that lack of non-protocol specified treatment

3.3.1.9. Minimum Residual Disease Rate (for Phase 2 R/R CLL only)

Minimal residual disease negative rate is defined as the proportion of subjects with MRD-negativity measured in the peripheral blood by flow cytometry (defined as <1 CLL cell per 10,000 leukocytes) by central lab.

If the subject's physical examination findings, laboratory evaluations, and radiographic evaluations suggest that PR, CR or CRi has been achieved, a peripheral blood by flow cytometry sample to evaluate MRD should be done between 8-12 weeks from the time of supportive clinical assessments including CT imaging of suspected PR, CR or CRi.

A peripheral blood sample testing for minimal residual disease (MRD) will be done at screening and end of treatment visit or if not taken at the EoT visit, then it can be drawn at SFU visit.

3.3.2. Safety variables

Please refer section 3.2.2 as same safety variables will be applied for Phase 2. As for clinical laboratory assessments, some additional laboratory tests will be required for CLL subjects in phase 2 – cohort B only, more detailed information please refer Table 4.

3.3.3. Pharmacokinetic variables

In Phase 2 portion, the schedule of sparse PK sampling for determination of acalabrutinib plasma concentration is presented in Table 13 of CSP.

4. ANALYSIS METHODS

4.1. General principles

The below mentioned general principles will be followed throughout the study:

- Descriptive statistics will be used for all variables, as appropriate. Continuous variables will be summarized by the number of observations, mean, standard deviation, median, upper and lower quartiles minimum, and maximum. For log-transformed data it is more appropriate to present geometric mean, coefficient of variation (CV), median, minimum and maximum. Categorical variables will be summarized by frequency counts and percentages for each category.
- Unless otherwise stated, percentages will be calculated out of the population total for the corresponding treatment group.
- For continuous data, the mean and median will be rounded to 1 additional decimal place compared to the original data. The standard deviation will be rounded to 2 additional decimal places compared to the original data. Minimum and maximum will be displayed with the same accuracy as the original data. While please refer section 4.2.6 for precision and rounding rules for pharmacokinetic data.
- For categorical data, percentages will be rounded to 1 decimal place.
- SAS® version 9.1 (*as a minimum*) will be used for all analyses.

In general, for all endpoints the last observation before the first dose of study treatment will be considered the baseline measurement unless otherwise specified. For assessments on the day of first dose where time is not captured, a nominal pre-dose indicator, if available, will serve as sufficient evidence that the assessment occurred prior to first dose.

Assessments on the day of the first dose where neither time nor a nominal pre-dose indicator are captured will be considered prior to the first dose if such procedures are required by the protocol to be conducted before the first dose.

In all summaries change from baseline variables will be calculated as the post-treatment value minus the value at baseline. The percentage change from baseline will be calculated as (post-baseline value - baseline value) / baseline value x 100. (If applicable add: For any variable subjected to log transformation, the change from baseline calculated and summarized on the log scale will be back-transformed and presented as a 'baseline scaled ratio' (BSR). Percentage change will then be calculated as (BSR - 1) x 100.)

Data will be presented separately for three cohorts:

- Phase 1 patients
- R/R MCL patients (Phase 1 and Phase 2 combined)
- R/R CLL patients (Phase 2 only)

Demographic data, exposure and safety data will be analyzed based on safety analysis set. Pharmacokinetics will be analyzed based on PK analysis set. Efficacy analyses will be analyzed on tumor response analysis set.

The method for handling missing data is described in the definition for each of the endpoints. Every effort will be made to obtain complete dates for deaths. In the event of a partial or missing death date, the algorithm in Appendix 8.4 will be used.

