1.3. Number of subjects

The primary objectives of Phase 1 portion are to evaluate the safety, tolerability and pharmacokinetics (PK) of acalabrutinib. Hence approximately 12 patients will be enrolled in Phase 1 to obtain adequate pharmacokinetic and safety data. Additional patients may be enrolled to ensure at least 8 eligible patients with evaluable single- and multiple-dose PK profiles based on China regulatory considerations.

For Phase 2 of the study, approximately 33 R/R MCL subjects (Cohort A) and 60 R/R CLL subjects (Cohort B) will be enrolled in order to evaluate the efficacy in R/R MCL and R/R CLL subjects. For Cohort A, a sample size of 33 subjects will provide a 95% two-sided confidence interval centered around an expected ORR of 80% that excludes an ORR of 60% as a lower bound. With 60 subjects from Cohort B, an exact binomial test with a nominal one-sided 2.5% significance level will have 90% power to detect the difference between a null hypothesis ORR of 70% and an alternative ORR of 88%.

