2. ANALYSIS SETS

2.1. Definition of analysis sets

For purposes of analysis, the following populations are defined:

Analysis set	Description
Safety analysis set	All subjects who received at least one dose of acalabrutinib.
Pharmacokinetics analysis set	All subjects who received at least one dose of acalabrutinib, for whom with reportable acalabrutinib plasma concentration and PK parameter data with no important protocol deviations that may impact PK.
Tumor response analysis set	All subjects who received at least one dose of acalabrutinib and for whom baseline tumor assessment is available.

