4.2.2.2. Overall response rate (ORR)

Primary analysis of BICR-assessed ORR will be conducted on the tumor response analysis set for MCL patients (phase 1 and phase 2 combined) and R/R CLL patients (phase 2) separately. ORR and the corresponding 95% two-sided CI of ORR will be presented based on Clopper-Pearson exact method. BICR-assessed ORR+PRL and the corresponding 95% two-sided Clopper-Pearson CI will also be presented.

.For MCL patients (phase 1 and phase 2 combined), maximum percentage changes from baseline in the sum of product diameters (SPD) will be presented using waterfall plots (tumor response marked with different colors) based on BICR assessments.

Analysis of investigator-assessed ORR, ORR+PRL and SPD will be conducted on the tumor response analysis set using same statistical methods. The concordance between investigator-assessed and BIRC-assessed ORR as well as CR and PR rates will be summarized for MCL cohort. The concordance between investigator-assessed and BIRC-assessed ORR, CR or CRi rate and ORR+PRL rate will be summarized for CLL cohort.

Subgroup analysis

Additionally, subgroup analysis following the categories as below will be performed where deemed appropriate, these will be summarized and presented on a forest plot including the BICR-assessed ORR and 95% CI.

- Age at enrolment (<65 versus ≥ 65 ; <75 versus ≥ 75)
- Sex (male versus female)
- ECOG (0 versus 1 versus ≥ 2)
- Bulky disease (longest diameter of lymph node <5 cm vs. ≥ 5 cm and <10 cm vs ≥ 10 cm at baseline)
- Number of previous lines (1 versus 2 versus ≥ 3)
- Extranodal disease (yes versus no) – MCL only
- Bone marrow involvement (yes versus no) – MCL only
- Gastrointestinal disease (yes versus no) – MCL only
- Simplified MCL international prognostic index (MIPI) (low risk [0-3] vs intermediate risk [4-5] vs high risk [6-11]) – MCL only
- Refractory disease at baseline (yes versus no)
- Ann Arbor lymphoma staging (1-3 versus 4) -MCL only
- Rai staging at baseline (0-II versus III-IV) - Phase 2 cohort B only
- $\beta 2$ -microglobulin at baseline (≤ 3.5 mg/L vs. >3.5 mg/L) – Phase 2 cohort B only
- IGHV mutation (mutated versus unmutated) – Phase 2 cohort B only
- 17p deletion (yes versus no) – Phase 2 cohort B only
- 11q deletion (yes versus no) – Phase 2 cohort B only
- TP53 mutation (mutated versus unmutated) - Phase 2 cohort B only

In addition, same the subgroup analysis will be presented for the investigator assessed ORR.

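### The efficacy set drops dosed subjects with no baseline tumor assessment from ORR and, without a reason, from OS and TTNT, and it conflicts with the PFS censoring rules

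*SAP*

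**What the plan says.** SAP 2.1 defines the tumor response analysis set as "All subjects who received at least one dose of acalabrutinib and for whom baseline tumor assessment is available". The safety analysis set in the same section has no scan condition: "All subjects who received at least one dose of acalabrutinib".

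SAP 4.1 then places all efficacy work on the smaller set: "Efficacy analyses will be analyzed on tumor response analysis set". SAP 4.2.2.2 repeats this for the primary endpoint: "Primary analysis of BICR-assessed ORR will be conducted on the tumor response analysis set". SAP 4.2.2.4 names the same set for DoR. SAP 4.2.2.8 (OS) and 4.2.2.9 (TTNT) refer back to the DoR method and name no other set. The Protocol agrees in its synopsis, 9.3, 9.4 and, for the primary ORR, 9.4.4.

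Three other provisions bear on the point:

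- **PFS.** Table 6 in SAP 3.3.1.4 has a row for "No baseline tumor assessments and it's not known to have died in 2 consecutive visits of baseline", censored at first dose. The text above the table also provides for subjects with no baseline assessment.
- **Missing post-baseline response.** SAP 3.3.1.1 assigns a best response of NE, and SAP 3.3.1.2 takes ORR as a proportion of the whole set, so these subjects remain as non-responders.
- **Sensitivity.** No all-dosed efficacy analysis is planned. The only ORR sensitivity analysis mentioned (SAP 2.2) is optional and would remove further patients.

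**The concern.** A single-arm response rate depends directly on its denominator. Here missing data are handled in two ways: a subject with no post-baseline assessment counts as a failure, while a subject with no baseline assessment disappears.

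For OS and TTNT the scan condition has no function. Both start at first dose (SAP 3.3.1.7 and 3.3.1.8) and end at death, or at next treatment or death. Protocol 7.2 requires survival status to be re-checked at final analysis for the whole safety analysis set, yet OS is then estimated on a subset of it.

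For PFS, the set and the censoring table cannot both be followed as written. The PFS text keeps as events those subjects without a baseline who die within two visits. The set definition removes them before the rule is reached.

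At stake are a possible upward shift in ORR close to the decision boundary, the loss of known events from OS and TTNT, and a PFS analysis that two programmers could build differently.

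**Working it through.** **Inputs.** From SAP 1.3: Cohort B n = 60; "an exact binomial test with a nominal one-sided 2.5% significance level"; null ORR 70%; alternative 88%; stated power 90%. From SAP 4.2.2.2: 95% two-sided Clopper-Pearson interval.

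**Formulas.**
- Exact one-sided p for x responders among n: P(X ≥ x | n, 0.70).
- Clopper-Pearson lower limit: the 2.5% quantile of Beta(x, n − x + 1). It exceeds 70% when the exact p is below 0.025, so the planned interval and the test in the sample-size text give the same decision.

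**Step 1: reproduce the plan.** For n = 60, the smallest x with p ≤ 0.025 is 50. Exact alpha is 0.0139, and power is P(X ≥ 50 | 60, 0.88) = 0.9006. The stated 90% is reproduced.

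**Step 2: change the denominator.** The dropped subjects are taken to be non-responders in the all-dosed count.

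| Responders / n | ORR | Exact p | Lower limit | 70% excluded? |
|---|---|---|---|---|
| 49/60 (all dosed) | 81.7% | 0.0295 | 69.6% | no |
| 49/59 (one dropped) | 83.1% | 0.0167 | 71.0% | yes |
| 48/60 (all dosed) | 80.0% | 0.0568 | 67.7% | no |
| 48/59 (one dropped) | 81.4% | 0.0349 | 69.1% | no |
| 48/58 (two dropped) | 82.8% | 0.0201 | 70.6% | yes |

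The bar is 50/60 with nobody dropped, 49/59 with one and 48/58 with two. One exclusion therefore changes the decision only at exactly 49 responders.

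**Step 3: how likely is exactly 49 of 60?**
- At ORR 70%: P(X ≥ 49) − P(X ≥ 50) = 0.0295 − 0.0139 = 0.0156, about 1.6%.
- At ORR 88%: 0.9491 − 0.9006 = 0.0485, about 4.8% on unrounded values.

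Each must be multiplied by q, the chance that one such subject is excluded. The documents do not give q. Over the full range 0 to 1, the probability of a reversal runs from 0 to 1.6% at 70%, and from 0 to 4.8% at 88%.

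**Step 4: worst-case type I error over the 60 dosed.** If one non-responder were always dropped, it would be P(X ≥ 49 | 60, 0.70) = 0.0295. With two it would be P(X ≥ 48 | 60, 0.70) = 0.0568. The nominal level is 0.025. These are upper bounds, not expectations.

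**Step 5: Cohort A at its stated size.** 25/33 has lower limit 57.7% and 25/32 has 60.03%, against the 60% bound in SAP 1.3. The same boundary effect appears. The analysed MCL number may differ from 33, because Phase 1 MCL subjects are pooled in.

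**Step 6: OS, TTNT and PFS.** No arithmetic is needed. Following the references gives OS → DoR method → tumor response set, and TTNT → DoR method → tumor response set. The definitions of OS and TTNT use only the first dose date and the date of death or next treatment. Setting SAP 2.1 beside Table 6, the row for subjects with no baseline tumor assessment describes people whom 2.1 has already excluded.

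**The case against.** The strongest reply is that the affected group should be close to empty. Inclusion criterion 8 requires radiographically measurable disease, a baseline CT is due within 28 days before first dose, and Protocol section 5 forbids waivers. This stands, and it limits the practical size of the point.

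The set is also prespecified and stated consistently in both documents. Exclusions would be visible: SAP 4.2.4.1 tabulates subjects left out of each set, 4.2.3.3.8 summarizes and lists all deaths, and 4.2.5 summarizes later anticancer therapy. OS and TTNT are descriptive. So a reader should not infer that deaths would be hidden. They would be reported as safety data but missing from the survival curve.

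Other stronger readings are tempting and not supported:

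- **That non-evaluable subjects in general are dropped.** They are not. Missing post-baseline data give NE, and the subject stays in the denominator.
- **That the exclusion can only raise ORR.** This holds only if subjects without a baseline are set to non-response. Several complete-response criteria are absolute thresholds (node size, spleen length, PET score), so such a subject could in principle look like a responder.
- **That a failed Cohort B result is readily turned into a success.** The reversal needs exactly 49 responders and an exclusion. The 70% comparison is called nominal and appears only in the sample-size text; the analysis section plans an estimate with an interval.
- **That power is lost.** Exact power is 0.9095 at n = 59 and 0.9179 at n = 58, against 0.9006 at 60.
- **That the Table 6 row could never apply.** The Protocol asks for a relevant baseline and the SAP for an available one, and neither says whether BICR or the investigator decides. If set membership and the PFS row were judged on different sources, the row could apply. The documents do not say this, so the conflict remains on a plain reading.

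**Conclusion.** The point holds as a defect in the definition of the analysis set, with a small expected numerical effect. Three parts are established from the text: missing baseline removes a dosed subject from the ORR denominator; OS and TTNT inherit that exclusion although neither needs a scan; and the PFS rules provide for subjects whom the set leaves out.

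The effect on the Cohort B conclusion is confined to the boundary: at most about 1.6% (ORR 70%) or 4.8% (ORR 88%) for one exclusion, and less once the chance of an exclusion is applied. This rests on 60 dosed subjects with independent outcomes, and on the dropped subject counting as a non-responder in the all-dosed analysis. The documents do not support describing the plan as likely to reverse a result. They do support correcting it, because the correction removes a possible bias and an internal contradiction.

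**What to change.** 1. In SAP 2.1, 4.1 and 4.2.2.2, base the primary BICR-assessed ORR on all dosed subjects (safety analysis set, per cohort; for MCL, the pooled Phase 1 and Phase 2 subjects), with missing baseline counted as non-response. Keep the tumor response set as a supportive analysis. If the primary set is not changed, prespecify the all-dosed ORR as a sensitivity analysis.
2. In SAP 4.2.2.5, 4.2.2.8 and 4.2.2.9, name the safety analysis set for PFS, OS and TTNT explicitly instead of inheriting it from DoR. The Table 6 row for missing baseline then has subjects to apply to.
3. Wherever the tumor response set is retained, say whether BICR or the investigator determines that a baseline is available.
4. Make the matching change in the Protocol synopsis, 9.3, 9.4 and 9.4.4, or record the departure in SAP section 6, which now reports no changes. Editing the SAP alone would put the two documents in conflict.

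The cost is a short wording change in both documents and an ORR that may be slightly lower. No new data are needed. If no subject lacks a baseline, every result is unchanged.

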4.2. Analysis methods

4.2.1. Data cut-offs

There are two planned analyses for all subjects of Phase 1 portion and cohort A of Phase 2 portion.

The data cut-off for the 1st analysis will take place when both of the following two conditions are met

- Approximately 1 month after cycle 1 day 1 of the last subject in Phase 1 to allow required PK samplings at cycle 0 and cycle 1 are collected.
- Approximately 6 months after last R/R MCL subjects across both Phase 1 and Phase 2 to allow a minimum of two tumor assessments after first dose.

A Clinical Study Report will be prepared to summarize PK, safety and efficacy data for Phase 1 portion and/or cohort A of Phase 2 portion. R/R MCL subjects in Phase 1, if applicable, will be combined together with the subjects in cohort A of Phase 2 portion for MCL analysis.

The data cut-off for the 2nd analysis will take place approximately 14 months after last subject enrolled in both Phase 1 and cohort A of Phase 2. A Clinical Study Report Addendum including all subjects of Phase 1 portion and/or cohort A of Phase 2 portion will be prepared at that time.

Selected safety summaries might be generated for R/R MCL subjects across Phase 1 and Phase 2.

There are three planned analyses for R/R CLL subjects of cohort B of Phase 2 portion.

The data cut-off for the 1st analysis will take place when approximately 6 months after last R/R CLL subjects enrolled in Phase 2. A Clinical Study Report will be prepared to summarize efficacy, safety and PK data for cohort B of Phase 2 portion. Efficacy analysis of tumor response in R/R CLL will only be applied for R/R CLL subjects in Phase 2. Tumor response of R/R CLL subjects in Phase 1 may be listed separately.

The data cut-off for 2nd analysis will take place when approximately 12 months after last R/R CLL subject enrolled in Phase 2. A Clinical Study Report Addendum including R/R CLL subjects of cohort B of Phase 2 portion will be prepared at that time.

The data cut-off for 3rd analysis will take place approximately 24 months after last R/R CLL subject enrolled in Phase 2. A Clinical Study Report Addendum including R/R CLL subjects of cohort B of Phase 2 portion will be prepared at that time.

